6.3.3 Clinical Laboratory Tests

Laboratory values will be collected at all study visits up to and including Month 24 (with the exception of Erythrocyte Sedimentation Rate and C-Reactive Protein labs). For each clinical laboratory parameter, values at each time point will be categorized as “Low,” “Normal,” or “High” and then categorized as “Clinically Significant” or “Not Clinically Significant,” as determined by the investigator. Changes from screening, pre-implantation, 24 hours post implantation, and hospital discharge in these categories will be tabulated.

The number and percentage of subjects with Low, High, Clinically Significant Low, and Clinically Significant High results will be presented by visit for each parameter.

6.3.4 Vital Signs

For each vital sign, values at each time point will be categorized as “Low,” “Normal,” or “High” and then categorized as “Clinically Significant” or “Not Clinically Significant,” as determined by the investigator. Changes from screening, change from the day of spine surgery (as measured before the surgery) and change from hospital discharge at each visit will be summarized without formal statistical testing.

Summary statistics (N, mean, and SD) of each parameter will be presented by visit.

The number and percentage of subjects with Low, High, Clinically Significant Low, and Clinically Significant High results will be presented by visit for each parameter.

6.3.5 Physical Examination and Neurological Examination Results

Physical examination results will be classified into ‘Normal’, ‘Abnormal, Not Significant’, and ‘Abnormal, Clinically Significant’ categories, and summarized by body system. Results will be listed.

Neurological examination results will be classified into ‘Normal’ and ‘Abnormal’ categories, and summarized for 11 body systems. Five tendon reflexes will be scored on a five-point (0-4) scale for both the right and left side. Additionally, voluntary abdominal muscle contraction, hip adduction/adduction, and toe flexion/extension on the right and left sides will be scored into 0=‘absent’ and 1=‘present’. Scores will be tabulated by subject across time, and a change from absent to present will be considered an improvement in condition.

6.3.6 Beck Depression Inventory II

The Beck Depression Inventory II (BDI-II), created by Aaron T. Beck, is a 21-question multiple-choice self-report inventory, one of the most widely used psychometric tests for measuring the severity of depression. In its current version, the BDI-II is designed for individuals aged 13 and over, and comprises items relating to symptoms of depression such

as hopelessness and irritability, cognitions such as guilt or feelings of being punished, as well as physical symptoms such as fatigue, weight loss, and lack of interest in sex.

The BDI-II is scored by adding up the score (0—3) of each of the 21 questions, and the assessment of the scores are as described below.

- 0—13 Minimal depression
- 14—19 Mild depression
- 20—28 Moderate depression
- 29—63 Severe depression

A score of 17 or higher may indicate the presence of depression and further evaluation by a mental health professional should be considered. A subject who gives a rating of 2 or 3 on item 2 (hopelessness) or item 9 (suicide ideation) should be closely scrutinized for suicide potential.

The BDI-II will be used to assess the subject's mood at hospital discharge and at months 1, 2, 3, 6, and 12. Observed values for total score and changes from baseline will be presented. BDI-II results will be listed.

6.3.7 Subgroup Analysis

No subgroup analyses are planned for the Primary Endpoint Analysis.

Separate efficacy tabulations may be performed for the subjects enrolled prior to conversion of the study from a pilot study to a pivotal probable benefit study, if necessary. Additionally, if sufficient data are available, separate efficacy analyses may also be performed on the subset of pediatric subjects (under age 22 at time of enrollment).

Separate Safety Event tabulations may be performed for the subjects enrolled prior to conversion of the study from a pilot study to a pivotal probable benefit study, as necessary.

7. TESTING/QUALITY CONTROL PLAN AND SOFTWARE/SYSTEM

All statistical programs will be written in SAS[®] version 9.3 [9]. Statistical programs will be tested and reviewed for Quality Control (QC) by a second programmer/biostatistician not involved in the programming as per DP Clinical (DPC)'s standard operating procedure (SOP). In addition, DPC's SOP will be followed to ensure that the information is complete, consistent, and accurately reflects the data stored in Clinical Data Management System (CDMS) database. Further all tables, listings, and figures (TLFs) will undergo a QC process by an independent biostatistician/programmer to ensure that the information is complete, consistent, and accurately reflects the data stored in CDMS.

7.1 Programming Specifications for TLFs

Appendix 1 provides a list of all the TLFs that are planned to be produced.

7.2 Formatting Conventions

The following formatting conventions will be used to output TLFs:

- TLFs are outputted by SAS Output Delivery System (ODS) into Rich Text Files (RTF) format.
- Tables and Listings will include borders around all headings and data cells.
- Output will be in landscape orientation with margins of 1.5 inches on top, and 1 inch for right, left, and bottom.
- The default font to be in tables/listings/figures will be Courier New.
- Preferred and minimum font size:

Portion of Output	Preferred	Minimum
Page Header	10 pt	8 pt
Title	10 pt	8 pt
Column header	10 pt	8 pt
Cells	10 pt	8 pt
Footnote	10 pt	8 pt
Page Footer	10 pt	8 pt

- Data will be centered within columns when the maximum length of the data being displayed is less than or equal to the maximum width of the column

heading. When the maximum length of the data being displayed exceeds the maximum width of the column heading, the data will be left-justified.

- Column headings should be in initial capital characters. For numeric variables, include “unit” in the column heading when appropriate.
- In figures, axes will be labeled appropriately.

7.3 Standard Text Conventions

7.3.1 Header

All output (table, listing, or figure) will have the following header:

InVivo Therapeutics
Protocol: InVivo-100-101

Page xx of XX

All output will have the date and time (date and time output was generated) and internal page number in the footer. Tables/Listings/Figures should be internally paginated (i.e., page numbers should appear sequentially within each output).

7.3.2 Title

At least three (3) lines, in general, will be reserved for the entire title.

- The first line is for the table/listing/figure number;
- The second line is for the actual title; and
- The third line is reserved for the analysis population descriptor.

All titles will be centered, as shown in the following example:

Table 14.3.2.1
Overall Incidence of Safety Events
Safety Population

7.3.3 Footnotes

Unless otherwise specified, footnotes will appear on all pages within the tables and listings as follows:

- Footnotes will be in the format of “Note: followed by 2 spaces, then the footnotes”, as shown in the following example:

Note: SD = Standard Deviation; SEM = Standard Error of the Mean.

- Each line of a complete footnote should end with a period.
- When an abbreviation (e.g. TESE, SAE, ITT, etc.) appears first time in the whole set of TLFs for a study, a footnote should be provided at least once; and it is up to the study statistician, to decide whether there is a need to repeat the same footnote for the rest of TLFs.
- A footnote serves as a brief explanation/clarification /definition /concept of a flag symbol or a character, an abbreviation, a terminology, etc., that appears in or relates directly to the displayed content of a table/listing/figure.
- Footnotes will not contain detailed/technical elaboration of, for example, a mathematical/statistical formula, a statistical term/test, or an algorithm for deriving a parameter value, which should be addressed in the text of the SAP.
- All footnotes will be at the lowest line of the page immediately above the footer. There will be one space between the last footnote and the footer.
- For Tables, first footnote will provide source listings and/or analysis datasets names for cross-referencing.

7.3.4 Footer

The following footer should appear at the very bottom of each page of a table, a listing, or a figure generated in SAS in the lower left corner:

Program: PGMNAME.sas; Creation Date and Time: MMDDDDYYYY HH:MM
Data Cutoff: DDMMYY:HH:MM:SS – Output Generated MMM DD, YYYY

where PGMNAME = SAS program name.

7.4 Statistical Conventions

7.4.1 Statistics Reported

- Unless otherwise specified, the mean and standard deviation (SD) will be displayed to one more decimal place than the original value, while minimum and maximum will be reported in the format of the original data, e.g.:

Original: xx

Mean and SD: xx.x

Minimum and maximum: xx

- Descriptive statistics in this template include: **Mean, Median, Standard Deviation (SD), Minimum, Maximum, and N**. In addition, 95% CI will be presented when appropriate.
- Unless specified in the actual TLF shells for a study, all percentages will be rounded to 1 decimal place in all tables/listings/figures. Rounding will take place after all calculations have been performed.
- Use of N versus n:
 - N = total number of subjects or subjects in the population.
 - n = total number of subjects or subjects in the specific category.

7.4.2 SAS Procedure Output

If appropriate, SAS procedure output may be formatted and saved as source for references and will be included in Appendix.

7.4.3 Tables Summarizing Categorical Data

The following specifications apply to tables that summarize categorical data:

- Percent of events should be left blank (including the parentheses) if the number of events is zero.
- If the categories of a parameter are ordered, then all categories between the maximum possible category and the minimum category will be included, even if $n=0$ for a given category between the minimum and maximum level for that parameter.
- If the categories are not ordered, then only those categories for which there is at least one subject represented will be included.
- A missing category will be added to any parameter for which information is not available for any subjects.

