4.4 Safety Endpoints

Safety endpoints will include the following:

1. General safety assessments
 - Incidence of all safety events (AEs/ADEs) of any kind/seriousness
 - Incidence of all serious safety events (SAEs/SADEs)
 - Incidence of unanticipated ADEs (UADEs)
2. Incidence of the following safety events for assessment of the potential risk associated with the use of Scaffold
 - Scaffold migration or malposition
 - Untoward physiologic reaction to PLGA-PLL materials
 - Scaffold-related loss of motor or sensory neurologic function
 - Increased inflammatory response

- Persistent cerebrospinal fluid leak
 - Damage to adjacent structures post Scaffold implant
 - Re-operation or removal of the Scaffold
 - Hemorrhage into or around the spinal cord causing neurologic deficit or possible need for further surgery
 - Surgical infection
 - Increased anesthesia time

 - Adhesion between the spinal cord and dura
 - Postoperative symptomatic or asymptomatic intraspinal cyst or syrinx
 - Post-Scaffold implant on-ventilator time for subjects with sensory deterioration of 2 or more dermatomes determined by either ISNCSCI pinprick or light touch exam as compared to subjects without sensory deterioration of 2 or more dermatomes.
3. Incidence of the following safety events for assessment of the potential risk associated with neurosurgical procedures
- Soft tissue wound infection or dehiscence
 - Surgical injury to the cord

 - Cerebrospinal fluid (CSF) leakage
 - Progressive neurological deterioration beyond that normally expected
 - Bacterial meningitis
 - Cord abscess
 - Failure to alter the natural course of healing from a spinal cord injury
4. Incidence of the following safety events for assessment of the most common general risks of surgery and spinal surgery:
- Adverse reactions to the anesthetic
 - Post-operative pneumonia
 - Blood clots in the legs or elsewhere (deep vein thrombosis) that may travel to the lungs (pulmonary embolus)
 - Infection at the site of surgery
 - Blood loss during surgery requiring a transfusion

- Injury to the nerves or spinal cord resulting in pain or further paralysis
 - Instrumentation breaking, dislodging, or irritating the surrounding tissues
 - Pain from the surgery itself
5. Findings of clinical laboratory tests, including routine blood chemistry and hematology tests
 6. Findings from vital signs measurements
 7. New onset or worsening of depression by Beck Depression Inventory II (BDI-II)

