6.3.2 Safety Events

The Medical Dictionary for Regulatory Activities (MedDRA) (Version 17) [5] will be used to classify all safety events (AEs, ADEs, Safety Events of Interest [associated with the potential risk with the use of Scaffold, risk associated with neurological procedures, and general risks of surgery and spinal surgery] SAEs, SADEs and UADEs) with respect to system organ class (SOC) and preferred term (PT). ADEs will be considered any safety event that is at least possibly related to the Scaffold or the procedure to implant the Scaffold. The safety event dataset will be reviewed by the study team to identify all events and to group the identified events into different categories for the analysis, particularly the Safety Events of Interest.

Summary tables will provide the total number of safety events of each type (AEs, ADEs, Safety Events of Interest, SAEs, SADEs and UADEs, Safety Events Leading to Discontinuation) and the number and proportion of subjects with each type of safety event.

Events will be tabulated for the overall study period and separately for the 6- Month Primary Endpoint Follow-up period. Within each tabulation, subjects within the Safety Set that had a successful Scaffold implant will be tabulated separately.

The following tables will be produced:

- Topline Summary of All Safety Events
- AEs, SAEs by SOC, PT and Intensity
- ADEs, SADEs, and UADEs by PT and Intensity
- Safety Events of Interest by PT and Intensity

In addition, tables providing all AEs and SAEs by SOC, PT, and Intensity will be presented for the All Treated Set.

The calculation of safety event percent will be based on the number of subjects per safety event system organ class and preferred term, where:

Percent of Subjects Experiencing Each Safety Event =

$$\text{Number Subjects with Safety Event} * 100 / \text{Total Number of Subjects}$$

When tabulating a proportion, if a subject has multiple safety events classified to the same category, that subject will be tabulated once under the worst severity for that safety event category. Summary tables will be presented by seriousness and severity. All safety event information will be provided in data listings.

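### Named safety endpoints with no events get no summary row under the SAP's table rules, so their pre-specified incidence goes unreported and no confidence limit is committed

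*SAP*

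**What the plan says.** SAP 4.4 sets out three lists of named risks as safety endpoints, each measured as an incidence: "Incidence of the following safety events for assessment of the potential risk associated with the use of Scaffold" (item 2), "Incidence of the following safety events for assessment of the potential risk associated with neurosurgical procedures" (item 3) and "Incidence of the following safety events for assessment of the most common general risks of surgery and spinal surgery" (item 4).

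SAP 6.3.2 has the study team review the safety event data and asks it "to group the identified events into different categories for the analysis, particularly the Safety Events of Interest". The planned display is "Safety Events of Interest by PT and Intensity", which the appendix numbers 14.3.1.5.1 (0-24 months), 14.3.1.5.2 (0-6 months) and 14.3.1.5.3 (6-24 months). The only statistic defined is "Percent of Subjects Experiencing Each Safety Event", the number of subjects with the event times 100 over all subjects.

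SAP 7.4.3 governs every table of categorical data. For unordered categories: "If the categories are not ordered, then only those categories for which there is at least one subject represented will be included". For zero counts: "Percent of events should be left blank (including the parentheses) if the number of events is zero". Rows with n=0 are kept only for ordered categories. No table is exempted.

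On intervals, 6.3 describes the safety presentation as descriptive, and 7.4.1 leaves 95% confidence intervals to judgement without tying them to any table.

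**The concern.** The SAP fixes the list of risks in advance but lets the data decide which of them appear in the results. A named risk is an unordered category. If nobody has it, there is no preferred term to show and 7.4.3 removes the row. The pre-specified endpoint, an incidence, then has no reported value, although the correct value is 0 of N.

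Two things are at stake. First, a reader of the summary table cannot tell a risk that did not occur from one whose events were coded to terms the team did not assign to that risk. Several entries in 4.4 are descriptions rather than dictionary terms, for example damage to adjacent structures after implantation, so the assignment matters. Second, zero events in a small study is weak evidence of a low risk, and without a row nothing on the page says how weak. Safety is part of the primary objective (3.1.1) and is meant to support an HDE application (3.1.2).

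**Working it through.** **Tracing a risk with no events through the plan**

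1. SAP 4.4 item 3 names bacterial meningitis and cord abscess; item 2 names Scaffold migration or malposition. Each is to be reported as an incidence.
2. SAP 6.3.2 forms the groups from events that were identified. No event means nothing to group.
3. The table rows are preferred terms. No event means no preferred-term row.
4. SAP 7.4.3 would remove an empty unordered row even if a programmer created one. Its percentage rule applies to rows that survive: the count 0 can be shown but the percentage is blank.
5. The result is no 0/N and no percentage for that endpoint in the summary tables.

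**Does another rule rescue the row?** The percentage-rounding rule in 7.4.1 yields to the table shells; 7.4.3 contains no such clause, so a shell with fixed zero rows would conflict with it. For listings, 7.4.4 takes the opposite approach: a conditional listing with no qualifying subjects must print a message saying so.

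**How many entries are affected?** SAP 4.4 has 13 + 7 + 8 = 28 bullets in items 2 to 4. This is not 28 distinct incidences. CSF leak appears in items 2 and 3, and infection at or near the operative site appears in items 2, 3 and 4. One bullet compares on-ventilator time between two groups of subjects and is not an incidence. Cyst and spinal cord adhesion are also tabulated Yes/No by subject from MRI (6.2.2.4; Table 14.2.10.2).

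**What a zero is worth**

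The SAP gives no figure here, so there is none to reproduce. The tables use the Safety Set Excluding Screen Failures, whose N is not stated. Assumed range: 16, the size at which the Primary Endpoint Analysis Set was closed (3.2.1), to 36, the planned maximum enrolment (3.2.1). All subjects in the primary set have a successful implant, so the safety N should not be below 16.

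- Exact (Clopper-Pearson) two-sided 95% upper limit for 0 of N: 1 - 0.025^(1/N)
- Probability of no event when the true risk is p: (1 - p)^N

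| N | Upper limit for 0/N | P(no event), p = 5% | P(no event), p = 10% |
|---|---|---|---|
| 16 | 1 - 0.025^(1/16) = 20.6% | 0.95^16 = 44.0% | 0.90^16 = 18.5% |
| 20 | 1 - 0.025^(1/20) = 16.8% | 0.95^20 = 35.8% | 0.90^20 = 12.2% |
| 36 | 1 - 0.025^(1/36) = 9.7% | 0.95^36 = 15.8% | 0.90^36 = 2.3% |

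Even at the favourable end, zero events does not exclude a risk of almost 1 in 10.

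**The case against.** The strongest reply is that this is a display convention. Dropping empty rows is normal in preferred-term tables, which have no fixed frame. All safety events are listed, events are monitored at every visit from surgery onward, and the topline table gives counts for Safety Events of Interest as a type. Cyst and adhesion have by-subject MRI tables in which a No is explicit. The promised table shells are not shown and might fix the rows. Safety is declared descriptive, and 7.4.1 permits intervals.

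Much of this stands, and it rules out several stronger readings. A reader might infer that the SAP hides these risks altogether, or that their absence cannot be checked; the listings and the table N allow a check, though an indirect one. A reader might infer that all 28 bullets disappear; they overlap, one is not an incidence, and two have MRI tables. A reader might infer that the SAP bars confidence limits; it only fails to commit to any.

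The reply does not meet the narrower point. Open-ended preferred-term tables and pre-specified endpoints are different things, and only the latter are at issue. A listing shows the events that occurred; it does not report an incidence of zero for a named category or show that every relevant term was assigned to it. The topline row pools all Safety Events of Interest. Shells with fixed rows would contradict 7.4.3 as written.

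**Conclusion.** The point holds as a reporting defect. Followed literally, the SAP leaves any named 4.4 risk with no events without a summary row or a reported incidence, and it commits to no confidence limit for those that do have a row. This is clearest for risks such as Scaffold migration, bacterial meningitis and cord abscess, for which the planned list has no dedicated table.

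The size depends on the unstated safety denominator. Over the assumed 16 to 36, the upper limit for zero events runs from 20.6% down to 9.7%, and a true 10% risk would go unseen with probability 18.5% down to 2.3%. It is tempting to quote only the N=16 figures, but 16 is the size of an efficacy set restricted by deviations and visit completion, and the safety set may be larger.

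A reader might also infer that study success is affected. It is not: the 25% criterion concerns AIS grade, and no data, endpoint or analysis set changes. The change is worth making before the tables are produced.

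**What to change.** 1. In 7.4.3, exempt Tables 14.3.1.5.1 to 14.3.1.5.3 from the empty-category and blank-percentage rules.
2. Give each distinct incidence-type category in 4.4 items 2 to 4 a fixed row with n, N and %, showing 0 and 0.0% where none occurred, with preferred terms nested beneath. Document how overlapping bullets map to rows and which terms feed each row. Show the on-ventilator time comparison separately.
3. Add an exact (Clopper-Pearson) 95% interval to each category row of the 0-6 month table (14.3.1.5.2). N must be that table's own denominator, not the primary-set 16. Where 6.3.2 tabulates successfully implanted subjects separately, use the N of that column.
4. In the 0-24 and 6-24 month tables, show the number of subjects followed and do not present limits based on full N while follow-up is incomplete. Under 5.4 the primary analysis is run when the last primary-set subject reaches 6 months, so such limits would overstate precision.

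The cost is a short SAP amendment, a mapping table and a fixed row template. No new data are needed. The downside is longer tables and visibly wide limits.

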7.4.4 Subject Data Listings

In general, individual subject data listings should include all subjects with data. However, if a subject data listing includes only subjects who met a certain condition, and there were no subjects who met that condition, then a “message” will appear indicating that no subjects met the condition for inclusion in that listing.

